## Part 2: The pilot randomized control trial

Strategy: We will conduct a pilot RCT of 250 adolescent females at high risk of unintended pregnancy to receive either the 10-week texting program, [name], or standard discharge instructions. *We hypothesize that the texting program will be feasible, acceptable, and increase contraceptive initiation rates (our primary outcome).*

Setting: We will recruit patients from the pediatric ED at New York-Presbyterian Children's Hospital, which cares for over 50,000 patients per year. Patients are predominantly Hispanic, insured, and of low socioeconomic status.

Subjects: The eligibility criteria is the same as Study Part #1. Inclusion: (1) age 14-19 years and (2) sexually active with males in the past 3 months. Exclusion: (1) currently using any "effective" form of contraception (as defined by the World Health Organization and includes the Shot, intrauterine device, ring, implantable device, Patch, birth control pills, or sterilization), (2) do not own a mobile phone with texting, (3) are pregnant, (4) are too ill for participation per the attending physician, (5) are cognitively impaired, (6) do not live locally within the 5 boroughs, Westchester, Rockland, Nassau or Suffolk counties, (7) do not speak English or (8) want to "become pregnant in the next year."

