#### Study Procedures: (different than Part 1)

After a patient provides informed consent, participants will complete a baseline questionnaire (new version attached as a Document, which is a shorter version of Part 1 baseline questionnaire).

Participants will then be block-randomized into one of two arms, Text Messaging (TM) or Standard Referral (SR). Participants will receive a \$10 gift card.

After randomization, participants in the TM arm will receive the texting intervention. The server will store all libraries of branched-logic messages and responses. All ingoing and outgoing texts will be time-stamped, recorded, and accessible to investigators.

Patients randomized to the SR arm will receive a welcome text message and then standard medical care as decided by their emergency medicine physician.

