Data for secondary outcomes will also be collected via phone follow up and EMR review during month 3 and interactive text messaging at weeks 3 and 6. A baseline survey will collect information regarding demographics, reproductive and sexual history, prior medical care, and pregnancy intentions. Questions were adapted from the Youth Risk Behavioral Survey, National Survey of Family Growth, and written *de novo*.

Analysis: We will analyze both an intention-to-treat (ITT) population and per-protocol population. The ITT population will include all enrolled and randomized patients. The per-protocol population will only include participants who completed follow-up and, for those in the intervention group, excludes those who received none of the text messages. Acceptability and Feasibility: We will summarize outcomes related to feasibility and acceptability using standard descriptive statistics and conduct exploratory bivariable analyses to identify characteristics of participants who appear more likely to opt out of the study (in order to develop further retention strategies). Potential efficacy: We will calculate the absolute risk difference (ARD) between groups with exact test-based 95% confidence intervals. For the ITT analysis, the outcome for those lost to follow-up will be imputed conservatively as *contraception not initiated*. We will use the chi-square test to determine the potential effect of the intervention on contraception initiation. We will conduct exploratory multivariable logistic regression analyses to test if age group (older (18-19 years) versus younger (17 and younger)), ethnicity, race, prior family planning clinic visits, having a primary care provider, prior pregnancy, and prior use of contraceptives, potentially confound or modify the effect of texting on contraception initiation. We will also examine texting response rates over time and how this relates to contraception initiation. We will also measure changes in contraception knowledge and decisional conflict based on proportions.

Sample size: Using prior ED studies, we expect to enroll approximately 250 patients over 2 years. Accounting for a 20% lost to follow up rate, this would enable us to detect a 17% absolute increase in contraception initiation

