(assuming 17% in SR arm, based on prior data) with 80% power ( $p=0.05$ , two sided). We readily understand that the effect size is likely not to be this large. As this is a pilot trial (Phase II), our goal is to gather the preliminary data needed for a definitive, multi-center RCT grant application (Phase III). We also plan to enroll equal proportions of younger (aged 14-17) and older (aged 18-19) adolescents to verify our prior findings that age modifies the effect of the intervention, with younger teens more often initiating contraceptives than older teens.

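### For the ITT comparison, testing seven baseline variables as confounders of a randomised effect has no sound basis, and seven modifier tests on about 34-51 events carry about a 30% chance of a false positive

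*Combined protocol and SAP*

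**What the plan says.** The Analysis paragraph of Part 2 (under Outcomes and Data Sources) sets the efficacy result as an absolute risk difference with an exact test-based 95% confidence interval, plus a chi-square test. In the ITT analysis, participants lost to follow-up count as not having initiated.

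It then adds a model: "We will conduct exploratory multivariable logistic regression analyses to test if age group" and six further baseline variables (ethnicity, race, earlier family planning visits, having a primary care provider, earlier pregnancy, earlier contraceptive use) "potentially confound or modify the effect of texting on contraception initiation". No criterion for confounding is given, and no level for the interaction tests, multiplicity rule or limit on model terms. The text does not say whether the model is fitted to the ITT or the per-protocol population, although both are to be analysed.

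Allocation is random: "Participants will then be block-randomized into one of two arms, Text Messaging (TM) or Standard Referral (SR"). The sample size text gives the scale: "we expect to enroll approximately 250 patients over 2 years". On the detectable effect it says: "Accounting for a 20% lost to follow up rate, this would enable us to detect a 17% absolute increase in contraception initiation". The control rate behind that figure is given as "assuming 17% in SR arm, based on prior data".

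Age has a special place. Preliminary Studies reports that the earlier pilot RCT found age group to be an effect modifier (p=0.02), and the sample size section plans equal enrolment of the two age groups to verify this.

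**The concern.** There are three problems with the model as worded.

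- **The confounding question.** Randomisation removes systematic baseline differences between arms. What remains in the ITT comparison is chance imbalance, which the interval and test already allow for. A change between a crude and an adjusted estimate is therefore not evidence of confounding.
- **The scale.** The odds ratio is non-collapsible: if there is an effect, adding a covariate that predicts the outcome changes it even when that covariate is perfectly balanced. An analyst who compares crude and adjusted odds ratios can take this for confounding.
- **The number of modifier tests.** Seven interaction tests on few events, with no stated level or limit, can produce chance modifiers.

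The stake is what gets carried forward. The sample size section says the trial is to supply preliminary data for a definitive multi-centre RCT. The age finding from the earlier pilot already shapes enrolment here, so a modifier reported from this trial may well shape the next one.

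**Working it through.** **1. The plan's own figure.** Inputs: 250 enrolled, 20% lost, 17% v 34%, two-sided 0.05. The allocation ratio is not stated; 1:1 is assumed. Followed up: 250 × 0.8 = 200, or 100 per arm. With pooled rate 0.255:

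power = Φ[(0.17 − 1.96 × √(2 × 0.255 × 0.745/100)) / √((0.17 × 0.83 + 0.34 × 0.66)/100)] = 79.2%.

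This reproduces the stated 80%.

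**2. Events.**
- No effect: 200 × 0.17 = 34.
- Planned effect: 100 × 0.17 + 100 × 0.34 = 51.
- The ITT counts are the same if everyone lost is scored as not initiated and the medical record adds none. If the rates held in all 250, they would be about 43-64.
- If equal age enrolment had the pilot's age-specific rates, the no-effect rate would be (34.8% + 11.8%)/2 = 23.3%, or about 47 events in 200.

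**3. Events per term.** Arm plus seven covariates, counting each as binary, is 8 terms: 34/8 = 4.3 to 51/8 = 6.4. With all seven interactions there are 15 terms: 34/15 = 2.3 to 51/15 = 3.4. Both fall if race has more than two levels. The plan does not say that all interactions enter together.

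**4. Non-collapsibility.** The marginal odds ratio for 34% v 17% is (0.34/0.66)/(0.17/0.83) = 2.52. The pilot's age odds ratio is (8/15)/(9/67) = 3.97, about 4. Take equal age groups, perfectly balanced, with that age odds ratio in both arms and no interaction:

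| Arm | Older | Younger | Average |
|---|---|---|---|
| Standard referral | 8.1% | 25.9% | 17% |
| Texting | 19.3% | 48.7% | 34% |

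The odds ratio within either age group is (0.193/0.807)/(0.081/0.919), about 2.72. The shift is 2.72/2.52 = 1.08, or +8%, with no confounding at all. If instead all seven covariates have odds ratio 1.5, the conditional value is 2.62 (+4%); at 2.0 it is 2.82 (+12%). Those two values are assumed. With no treatment effect, or with covariates that do not predict the outcome, the systematic shift is zero.

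**5. How often a shift would be seen.** Simulated trials with no confounding built in (600 per scenario, n=200, covariate prevalences and odds ratios assumed) gave these shares with an odds ratio change above 10%:
- covariates not prognostic: 19-22%;
- every covariate odds ratio 1.5: 32-43%;
- every covariate odds ratio 2.0: 54-69%.

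The 10% cut-off is also assumed, since the plan gives none. The lower end of each range is the no-effect case, where shifts come from chance imbalance and sampling noise rather than non-collapsibility.

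**6. False modifiers.** Seven independent null tests at an assumed 0.05: 1 − 0.95^7 = 30%. Simulated one-at-a-time tests gave 22-31% (n=200 and 250). A model with all seven interactions showed separation in about 7-25% of runs at n=200.

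**7. Power for the age interaction.** Suppose texting raises initiation from 17% to 34% in younger teens only. The interaction odds ratio is then 2.52, with log 0.922. With 50 per age-by-arm cell the standard error is 0.717 and power is 25%. With 62.5 per cell (all 250) the standard error is 0.641 and power is 30%.

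**The case against.** The strongest reply is that the plan already calls this model exploratory, in a trial that describes itself as a pilot, and that the efficacy result is fixed elsewhere. This stands, and it limits the point to the secondary modelling. A reader might infer that the headline could move to an adjusted odds ratio chosen from the data; nothing in the plan provides for that.

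A reader might also infer that the odds ratio is bound to shift and that chance modifiers are bound to appear. The figures do not support either. The systematic shift needs both a real effect and prognostic covariates, and at about 30% most such trials would report no false modifier. If age is set aside as preplanned, six speculative tests remain: 1 − 0.95^6 = 26%.

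Chance imbalance in a prognostic variable is a recognised reason to look at an adjusted estimate. That is true, but it argues for fixed adjustment chosen in advance, not for a test of confounding.

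It would also be too strong to call covariate adjustment empty throughout. The per-protocol population drops participants without follow-up and, in the texting arm only, those who received no messages. Exclusions after randomisation can cause real confounding.

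Lastly, one might suppose that ethnicity hardly varies, because "Patients are predominantly Hispanic, insured, and of low socioeconomic status". The plan gives no percentage, so the point does not rest on this.

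What the exploratory label does not do is give the ITT confounding test a meaning, or supply the missing criterion, level and population.

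**Conclusion.** The point holds as a fault in an under-specified exploratory analysis. For the ITT comparison, the confounding test has no sound basis and can mislead: if texting works, the odds ratio can move by about 8% in balanced arms on adjustment for age alone, or by about 4-12% across the covariate strengths tried. Seven modifier tests carry about a 30% chance of at least one false positive on about 34-51 events.

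The age figure rests on the pilot's crude age rates, equal age groups and the planned 17% v 34%. The 4-12% range rests on assumed covariate odds ratios, and the 30% on an assumed 0.05 level and independent tests. The unadjusted risk difference, its interval and the chi-square test are unaffected. The change is worth making because it puts a clear estimate in place of a test with no interpretable result, at little cost.

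**What to change.** In the Analysis paragraph of Part 2:

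1. For ITT, remove the test for confounding. In its place prespecify one supportive adjusted risk difference, for example standardised from a logistic model. Use a short fixed list of prognostic baseline covariates that includes age group, fitted whatever imbalance is observed.
2. Name age-by-arm as the single prespecified interaction, in line with the pilot finding and the equal age enrolment. Report it as an estimate with an interval, given power of about 25-30% in the case worked above.
3. Report the other modifiers one at a time, as subgroup risk differences with intervals and no claim of significance.
4. State the population for each model. Covariate adjustment may be kept for the per-protocol analysis, with the reason given.

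The cost is a few lines of SAP text and code, and fewer exploratory p-values. The baseline variables are already collected, and sample size, conduct and the main analysis do not change.

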**Evaluating a conventional pregnancy prevention text messaging intervention:** We then conducted an ED-based pilot RCT of sexually active females aged 14–19, randomizing patients to receive 3 months of conventional pregnancy prevention texts versus standardized discharge instructions (IRB #AAAM3457). Of the 100 enrolled, feasibility and acceptability were high, with follow-up rates of 88%, 1172/1654 (70.9%) texts successfully delivered, and most (36/41; 87.7%) in the intervention arm wanting future health messages. While there was no signal to suggest a meaningful effect of the intervention for all ages, we identified age group as an effect modifier ( $p=0.02$ ). Overall, younger adolescents (age 14-17 years) initiated contraception more often than older adolescents (age 18-19 years) [34.8% (8/23) versus 11.8% (9/76);  $p=0.01$ ].

**Developing a user-informed, theory-based, personalized, interactive pregnancy prevention texting intervention:** (PI: [name]; Funding: Columbia University KL2 Career Development Grant) In January 2017, we were awarded a 2-year KL2 grant to design and program a personalized and interactive (two-way) pregnancy prevention texting intervention, targeting adolescents at high pregnancy risk using the ED for medical care. There is evidence to suggest that dynamic two-way text messaging interventions, such as those involving alcohol reduction and depression, can guide participants through the process of behavior change. Individually tailored messaging programs provide a sense of personalization and increases personal relevance, which is particularly important for adolescent behavior change.

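### The 17% control rate behind the Part 2 power statement appears to be the pilot's overall rate and was not standardised to the planned 50:50 age mix; on the pilot's pooled age rates, power for a 17-point increase is about 74%

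*Combined protocol and SAP*

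**What the plan says.** The sample-size paragraph closing the Part 2 section on outcomes and data sources (Combined protocol and SAP) sets enrolment by feasibility: "we expect to enroll approximately 250 patients over 2 years". It then states what that number delivers. "Accounting for a 20% lost to follow up rate", the text says "this would enable us to detect a 17% absolute increase in contraception initiation", and the condition attached is "assuming 17% in SR arm, based on prior data) with 80% power", at a two-sided 5% level. No study, arm or age group is named as the source of the 17%.

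The same paragraph adds: "We also plan to enroll equal proportions of younger (aged 14-17) and older (aged 18-19) adolescents". The reason given is to verify the pilot's result that age modifies the effect, with younger teens initiating more often.

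The only initiation counts in the document that could supply 17% are the pilot results under Preliminary Studies: "younger adolescents (age 14-17 years) initiated contraception more often than older adolescents (age 18-19 years) [34.8% (8/23) versus 11.8% (9/76". These are given for the whole pilot, not by arm. The pilot text reports no meaningful effect across all ages, but age as an effect modifier (p=0.02).

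**The concern.** A control rate used for planning should describe the population to be enrolled. The 17% agrees to rounding with the pilot's overall rate, and about three-quarters of that sample were aged 18-19, the group with the lower rate. Part 2 intends a much younger mix. The plan uses the age difference to choose the mix but does not carry it into the control rate stated just before.

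For a fixed absolute difference, a control rate nearer 50% means more variance and less power. If the control rate in the planned mix is above 17%, the stated power and detectable difference are somewhat too favourable. A 17% benchmark could also mislead when the observed control rate is judged, or when the definitive multi-centre trial is planned.

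**Working it through.** **Inputs.** Control rate 17%, increase 17 points, two-sided 5%, 80% power, 250 enrolled and 20% loss come from the sample-size paragraph. The pilot counts 8/23 and 9/76 come from Preliminary Studies. The allocation ratio is not stated ("Participants will then be block-randomized into one of two arms, Text Messaging (TM) or Standard Referral (SR")), so 1:1 is assumed. Evaluable per arm: 250 × 0.8 / 2 = 100, which is the plan's own basis.

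**Formula.** With p̄ = (p1 + p2)/2:

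power = Φ{ [ |p2 − p1| − 1.96 √(2p̄(1 − p̄)/n) ] / √([p1(1 − p1) + p2(1 − p2)]/n) }

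The detectable difference is the value of p2 − p1 at which this equals 0.80.

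**1. The plan's figure.** p1 = 0.17, p2 = 0.34, p̄ = 0.255, n = 100:
- null standard error √(2 × 0.255 × 0.745/100) = 0.0616
- alternative standard error √((0.1411 + 0.2244)/100) = 0.0605
- (0.17 − 1.96 × 0.0616)/0.0605 ≈ 0.81, so power is 79.2%

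With unpooled variance power is 80.3%. The detectable difference is 17.2 points (16.9 unpooled). The stated 80% and 17 points reproduce from their own inputs.

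**2. Likely source of the 17%.** (8 + 9)/(23 + 76) = 17/99 = 17.2%. Share aged 14-17: 23/99 = 23.2%.

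**3. Rate for the planned mix.** 0.5 × 34.8% + 0.5 × 11.8% = 23.3%.
- Standard error: √{0.25 × [0.348 × 0.652/23 + 0.118 × 0.882/76]} = 0.053
- Approximate 95% interval: 23.3% ± 1.96 × 5.3 points, or 13% to 34%

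**4. Power at that rate.** p1 = 0.233, p2 = 0.403, p̄ = 0.318:
- standard errors 0.0659 (null) and 0.0648 (alternative)
- (0.17 − 1.96 × 0.0659)/0.0648 ≈ 0.63, so power is 73.6% (74.7% unpooled; 74.2% by exact calculation for the uncorrected chi-square test)

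**5. Sensitivity to the control rate (pooled-variance formula, 100 per arm).**

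| Control rate | Power for +17 points | Detectable difference at 80% power |
|---|---|---|
| 16.2% | 80.0% | 17.0 points |
| 17% | 79.2% | 17.2 points |
| 20% | 76.3% | 17.9 points |
| 23.3% | 73.6% | 18.45 points |
| 25% | 72.5% | 18.7 points |
| 31.2% | 69.3% | 19.4 points |

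**6. How far pooling over arms matters.** The pilot's split by arm is not given, so splits were assumed: 38 older participants per arm, 11 or 12 younger in the control arm, and totals held at 8/23 and 9/76. Splits with an age-by-arm interaction p between 0.01 and 0.04 (the pilot reports 0.02) were kept.
- All such splits: the 50:50 control rate runs from about 11% to 37%, and power from 87% to 68%.
- Only splits with overall arm rates within about 3 points, in keeping with the pilot's lack of an overall effect: about 16% to 31%, and power from 80% to 69%.
- Low end: control 2/12 and 6/38 gives (16.7% + 15.8%)/2 = 16.2%. High end: control 6/11 and 3/38 gives (54.5% + 7.9%)/2 = 31.2%.
- Within this narrower set, splits in which texting did relatively better in the younger group give 16% to 18%; splits in the other direction give 28% to 31%. The pilot text does not state the direction in terms of arms.

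**The case against.** The strongest reply is that neither step in the argument is documented. The plan calls 17% a control-arm rate from prior data. The match with 17/99 is suggestive, but the pilot's control-arm rate is not reported. The 23.3% is not a control-arm rate either: it pools both arms, and the reported effect modification is a reason to doubt that the arms were alike within age groups. An assumed pilot split of 2/12 younger and 7/38 older in the control arm gives 17.5% at 50:50 and 78.6% power, so the stated figure could hold as it is. The interval around 23.3% also includes 17%. All of this stands, and it limits the point to a missing standardisation.

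A second reply is that power falls only because the absolute difference is held fixed. At the odds ratio implied by 17% versus 34%, (0.34/0.66)/(0.17/0.83) = 2.5, a 23.3% control rate corresponds to 43.3% on texting, with power of about 86%. This is correct, but the plan states its target as an absolute increase and its efficacy measure as an absolute risk difference, so the fixed difference is the plan's own basis.

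A third reply is that little turns on it. Enrolment is set by feasibility, the plan says that the true effect is probably smaller than 17 points, and the trial is a pilot. That bears on importance. It does not make the control rate right for the planned mix, and the plan says that its data will feed a definitive trial.

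**Conclusion.** The point holds as a missing standardisation. The power statement uses a control rate that appears to come from a sample 23% aged 14-17, for a trial planned at 50%, with no adjustment and no stated source. On the pilot's pooled age rates, the planned mix lowers power for 17 points by about 5.5 percentage points (79.2% to 73.6%) and raises the detectable difference by about 1.3 points (17.2 to about 18.5).

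This rests on 100 evaluable per arm, 1:1 allocation, a fixed absolute difference, and similar rates in the two pilot arms within each age group. The last assumption is the weak one.

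A reader might go on to infer that 17% is wrong, that 23% is the true control rate, or that the 17% assumption and the equal-age target contradict each other. The documents support none of these. They give no control-arm rates by age, and a 17% control rate and a 50:50 mix are compatible if those rates bear it out. Nor is the stated arithmetic at fault.

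**What to change.** In the Part 2 sample-size paragraph:

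1. State which study and which arm the 17% comes from.
2. Give the pilot's control-arm rates by age group, weight them 50:50, and restate the power and detectable difference at that rate.
3. If only rates pooled over arms are available, state a control rate of about 23% and a detectable increase of about 18.5 points with 80% power, labelled as an assumption. Add a sensitivity range wider than 17% to 25%. For example, 16% to 31% gives power for 17 points from about 80% to 69%, and a detectable difference from about 17 to 19 points.

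Keep the target of equal age proportions, since it is the plan's stated means of checking effect modification by age.

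The cost is a sentence or two and, probably, a slightly less favourable figure. Holding 80% power for 17 points from 23.3% would take 117 evaluable per arm, or 234/0.8 = 293 enrolled (rounded up), but that is not asked for: with enrolment set by feasibility, restating what 250 can detect is enough.

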### Recruitment (same as Part 1)

A member of the research team will identify potentially eligible patients using the electronic medical record (EMR) in the pediatric Emergency Department at New York-Presbyterian Children's Hospital of New York. Our EMR reveals the age of each patient. The research team member will ask the medical provider caring the patient to confirm eligibility criteria. If a patient is eligible, that provider will privately introduce the study and ask if a research team member can explain it further.

A member of the research team will then privately explain the study in full to the eligible patient in a private location by reviewing the informational form and answering all questions. We used Columbia University IRB-suggested language to design the informational sheet. As part of our information sheet, we will include the language of HIPAA Form B that will include the nature and scope of the PHI to which access is sought and certifications to be made by the researcher.

To ensure the protection or the rights and welfare of the minor, we will put a substitute process in place to verify the minor's willingness to participate. This will be in the form of a two-person verification (as suggested in IRB correspondence). These 2 people will be the research investigator/ coordinator consenting the patient and the medical provider caring for the patient in the ED (who is involving in the screening process).

Eligible patients will verify verbally their agreement to participation. No signatures will be collected. All participants will receive a copy of the informational sheet.

We will explain that we are not responsible for the costs of the texts but do compensate with a gift card. Based on our prior work, the vast majority of our ED adolescent population has unlimited texting on their phones.

We have experience enrolling adolescents into sexual health studies when their parents are present and are able to maintain confidentiality. By explaining the study as a sexual health study aiming to educate adolescents in our community, we are able to discuss the study to both the parent and adolescent. We then talk to the adolescent in private, explain that she was selected because she is at risk of getting pregnant.

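### Age group should be carried into the Part 2 efficacy test, with age-stratified blocks alongside: a free improvement, not the correction of an error

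*Combined protocol and SAP*

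**What the plan says.** - **Enrolment (Part 2, Sample size paragraph):** "We also plan to enroll equal proportions of younger (aged 14-17) and older (aged 18-19) adolescents". The stated purpose is to verify that age modifies the effect.
- **Prior evidence (Preliminary Studies, conventional texting pilot):** "we identified age group as an effect modifier", with p=0.02. Younger teens "initiated contraception more often than older adolescents (age 18-19 years) [34.8% (8/23) versus 11.8% (9/76"), p=0.01. These rates combine the two arms; rates by arm and age are not given.
- **Availability of age (Part 2, Recruitment):** "Our EMR reveals the age of each patient".
- **Allocation (Part 2, Study Procedures):** "Participants will then be block-randomized into one of two arms". No stratification factor is named.
- **Efficacy analysis (Part 2, Analysis paragraph):** "We will use the chi-square test to determine the potential effect of the intervention on contraception initiation", and "We will calculate the absolute risk difference (ARD) between groups with exact test-based 95% confidence intervals". Neither is stratified or adjusted.
- **Where age appears in the analysis:** in an exploratory logistic regression, as one of seven factors examined to see whether they "potentially confound or modify the effect of texting on contraception initiation".

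**The concern.** An enrolment target fixes the age mix of the trial as a whole. It does not balance age between the arms. If age predicts initiation as strongly as the pilot suggests, two things follow from leaving it out of allocation and out of the headline test.

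First, variation due to age stays in the error term of the chi-square test, which costs some power. Second, a chance excess of younger teens in one arm moves the unadjusted ARD, and the test result with it, for reasons unrelated to texting. The trial is meant to supply preliminary data for a definitive multi-center application, so the ARD is one of its main products.

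**Working it through.** **1. The plan's own figure.** Inputs from the Sample size paragraph: 250 enrolled, 20% loss (100 evaluable per arm, taking 1:1 allocation), 17% vs 34%, two-sided 0.05. With pooled rate 0.255:

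Power = Φ{[0.17 − 1.96 × √(2 × 0.255 × 0.745 / 100)] / √[(0.17 × 0.83 + 0.34 × 0.66) / 100]} = 79.2%.

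The stated 80% reproduces.

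**2. Age and initiation in the pilot.** 8/23 = 34.8%; 9/76 = 11.8%; ratio 2.94, approximate 95% CI 1.28 to 6.74. Odds ratio = (8 × 67) / (15 × 9) = 3.97. The difference is 23.0 points.

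**3. Chance imbalance.** With half the sample younger and blocks that ignore age, the number of younger teens in the texting (TM) arm is hypergeometric. The chance of a difference of at least 10 points in either direction is 12.9% with 125 per arm and 20.3% with 100 per arm. Each 10 points shifts the unadjusted ARD by 0.10 × 23.0 = 2.3 points.

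**4. Consequence of such an imbalance (125 per arm, pilot rates, no true effect).** The smallest possible imbalance of at least 10 points is 69 vs 56 younger teens. With the excess in the TM arm:

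| Test | Favouring texting | Other direction | Two-sided |
|---|---|---|---|
| Unadjusted chi-square | 5.7% | 0.6% | 6.3% |
| Mantel-Haenszel by age | 2.5% | 2.5% | 5.0% |

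**5. Power (100 per arm).** Control rates are set at 34.8% and 11.8%, with 50:50 age enrolment, 400,000 simulated trials per scenario and no continuity correction. For age stratum k, with x_k initiators in TM, m_k initiators in all, n_1k and n_0k participants per arm and N_k in total, the stratified test is

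Z = Σ(x_k − n_1k m_k / N_k) / √Σ[n_1k n_0k m_k (N_k − m_k) / (N_k²(N_k − 1))].

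| Effect, younger / older (points) | Age-blind blocks, chi-square (current plan) | Age-stratified blocks, Mantel-Haenszel |
|---|---|---|
| +17 / +17 | 74.2% | 76.7% |
| +34 / 0 | about 74.5% | about 82.6% |
| 0 / +34 | about 74.5% | about 74.3% |

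The starting value is below 79.2% only because the pooled pilot rates average (34.8 + 11.8)/2 = 23.3% rather than 17%; the comparison across each row is what matters. Keeping the control rate at 17% overall with the pilot odds ratio (25.9% younger, 8.1% older), and an effect through a common odds ratio, gives 79.5% to 82.6%. If age does not predict initiation and the effect is equal, the result is 79.5% to 79.6%, so nothing is gained or lost.

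**6. Which half of the change does the work.** For +17/+17, the Mantel-Haenszel test with age-blind blocks already gives 76.4%; stratified blocks add about 0.3 points. Stratified blocks with the unadjusted chi-square give about 75.0%, which is about 2 points below Mantel-Haenszel but not below the current plan. Type I error is then about 4.3% (124 per arm), against 5.0% for Mantel-Haenszel.

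**The case against.** The planned analysis is not wrong. Over repeated randomisations the unadjusted chi-square keeps its error rate (5.2% in simulation at 124 per arm). The trial is described as a pilot, and the Sample size paragraph concedes that the true effect is probably smaller than 17 points, so power at +17 is not decisive. Age is already in the exploratory regression, which would help to expose a chance imbalance. The gain is modest, and the pilot contrast rests on 17 events with the arms combined, so part of it may reflect effect modification rather than prognosis.

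All of that stands, and it limits the point to an improvement. It does not remove it: the headline test and ARD remain unadjusted whatever the regression shows, and the change costs almost nothing.

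Two stronger readings are tempting. One is that the chi-square has an inflated false-positive rate. The 6.3% applies only given one particular imbalance, so this does not follow. The other is that the stated power is too high, because 17% resembles the pilot's overall 17/99 = 17.2% from a sample with 23/99 = 23% younger teens, while 50:50 enrolment would give 23.3%. The documents do not support that. They attribute the 17% only to prior data, they do not give the pilot's standard-referral (SR) rates by age, and 23.3% comes from both arms combined. The SR rate at a 50:50 mix cannot be settled from them, and the stated power reproduces on its own inputs.

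**Conclusion.** The point holds as a free improvement. Moving age into the primary efficacy test is the part that matters; stratifying the blocks accompanies it and prevents chance age imbalance at randomisation. The gain is about 2.5 power points if texting works equally in both age groups and about 8 if it works only in younger teens. It is about zero if age is not prognostic and the effect is equal. The largest loss seen is about 0.3 points, when the effect is wholly in older teens.

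These figures assume 1:1 allocation, an exact 50:50 age split, loss unrelated to age or arm, blocks otherwise random with respect to age, and (except in the 17% variants) control rates equal to the pooled pilot rates. If age stratification is already intended but unstated, the allocation part needs only a sentence, while the analysis change becomes more necessary.

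**What to change.** 1. **Analysis paragraph (main change).** Suggested text: *The primary efficacy test for contraception initiation will be a Mantel-Haenszel test stratified by age group (14-17, 18-19). The Mantel-Haenszel-weighted absolute risk difference will be reported with its 95% confidence interval. The unadjusted chi-square test and risk difference will be supportive.* Name the interval method for the weighted difference, since the exact method now specified goes with the unadjusted one. The exploratory regression can stay as it is.
2. **Part 2 Study Procedures (accompanying change).** Suggested text: *Randomisation will be in blocks, stratified by age group (14-17, 18-19).* This should not be adopted without the first change, because the unadjusted chi-square would then be conservative.

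Cost: two randomisation lists instead of one and a few lines of wording. There are no extra participants and no new data, and the sample size is unchanged.
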